1.1. State of the art

Electronic cigarettes (e-cigarettes) are increasingly popular worldwide. About 5% of adults in the western world are current users.¹ The liquid (e-liquid) carriers vaporized are composed of propylene glycol (PG) and glycerol (GLY), which transport nicotine and/or flavorings.² Regular e-cigarettes users purchase last generation devices delivering high energy level to low coil resistance.³ High energy settings are used to increase heat and vapor production,⁴ to enhance the throat and nicotine hits,⁵ whilst nicotine concentration in the e-liquid is strongly reduced through time. E-cigarettes with high output wattage increase the quantity of e-liquid consumed per puff, and produce volatile carbonyls by thermal degradation.⁴ Daily exposures to large amounts of high temperature PG/GLY aerosol may present a hazard to health.

1.2. Study of acute vaping effects on cardiorespiratory parameters (2016-2017)

We found that acute PG/GLY mix (50:50) inhalation: 1) induced a sustained transcutaneous hypoxia without modifying carbon dioxide (CO₂) tension; 2) decreased hemoglobin oxygen saturation, as assessed by fingertip pulse oximeter; 3) injured the lower airway, as reflected by urine and serum club cell protein 16 (CC16) rises,⁶ and small airway constriction during lung function tests.⁷

1.3. Study of acute nicotine free vaping effects on arterial O₂ concentration (2017-2018)

At our knowledge, we are the first to demonstrate that acute high wattage PG/GLY vaping induces transcutaneous hypoxia. Transcutaneous hypoxia has been described with tobacco smoking, as a consequence of nicotine-induced vasoconstriction,⁹ but effects of a nicotine free PG/GLY liquid vaporization on this parameter were unknown. Tissue oxygen (O₂) and CO₂ tensions reflect the delivery of O₂ and the extraction of CO₂, which are both dependent on respiratory and microcirculatory functions.¹⁰ The decrease in underlying dermal O₂ levels could be explained by: 1) a decrease in arterial O₂ concentration; 2) changes in hemodynamic parameters; and/or 3) microcirculatory endothelial dysfunction.¹⁰ Our current experiments are focusing on acute effects of PG/GLY vaping on arterial O₂ concentration, namely, concentration of hemoglobin, O₂ saturation of hemoglobin and its biological determinants and arterial O₂ partial pressure.¹¹⁻²

1.4. Studying the reversibility of PG/GLY aerosol effects on lungs in regular e-cigarettes users

Our new working hypothesis is that high temperature vaping deposits a hot and moist large amount nanoparticulate PG/GLY aerosol deeply in the lungs,¹³ resulting in small airways inflammation and constriction,¹³ rheological surfactant and mucus properties disturbances,¹⁴ small bronchioles and alveoli collapses,¹⁴ arterial oxygenation impairments, which decrease hemoglobin-oxygen saturation and induce the tissue hypoxia we observed.¹⁰

In order to verify the new hypotheses aforementioned on PG/GLY vaping induced-lung gas exchanges perturbations and its reversibility, as well as to disentangle respective effects of PG/GLY and nicotine, we will test effects of vaping cessation in regular e-cigarettes users by means of classical cardiorespiratory parameters assessments,¹⁷⁻¹⁹ lung function tests with diffusing capacity analysis and a maximal cycle ergospirometer test.²⁰ Lastly, quantitative discovery serum proteomics²¹ and metabolomics²² in the serum, urine and exhaled breath

condensate will be performed with the view to highlight biomarkers associated with chronic high wattage vaping exposition.

2. Goals of the research

This research proposal tests the following hypothesis regarding the reversibility of PG/GLY and PG/GLY plus nicotine vaping in regular e-cigarettes users

A. In comparison to pursuit of PG/GLY vaping with or without nicotine, e-cigarette cessation for five days:

- Increases transcutaneous O₂ tension and O₂-haemoglobin saturation
- Decreases respiratory rhythm
- Increases lung diffusing capacities and forced expiratory flows
- Increases maximal rate of oxygen consumption during cycle ergospirometer test
- Modifies heart rate variability
- Decreases arterial stiffness
- Decreases serum PG/GLY and nicotine concentrations

B. In comparison to PG/GLY vaping with nicotine, e-cigarette cessation for five days or PG/GLY vaping:

- Increase cutaneous vascular conductance and decrease arterial stiffness
- Increase acetylcholine and heat mediated vasodilation

C. Each of the three experimental sessions (e-cigarette cessation, PG/GLY vaping and pursuit regular consumptions):

- Induces specific serum, urine and exhaled breath condensate metabolomics profiles
- Induces specific serum proteomics profile

This research proposal tests also the following hypothesis regarding acute effects of PG/GLY vaping with and without nicotine in regular e-cigarettes users:

A. In comparison to baseline, PG/GLY vaping without nicotine:

- Decreases transcutaneous O₂ tension and O₂-haemoglobin saturation
- Increases respiratory rhythm
- Increases serum PG/GLY concentrations
- Induces specific serum, urine and exhaled breath condensate metabolomics profiles

B. In comparison to baseline and PG/GLY without nicotine, PG/GLY vaping with nicotine:

- Decreases transcutaneous O₂ tension and O₂-haemoglobin saturation
- Decrease continuous vascular conductance and increase arterial stiffness
- Increases respiratory rhythm
- Increases serum PG/GLY and nicotine concentrations
- Induces specific serum, urine and exhaled breath condensate metabolomics profiles

3. Methodology

3.1. Participants, interventions, periods and randomization

The participants, who are exclusive vapers since at least one years, will undergo three experimental periods in a random order: e-cigarettes cessation for five days (**cessation session**), nicotine free vaping for five days (**nicotine free session**), regular e-cigarettes consumption (**regular consumption session**). Baseline clinical cardiorespiratory parameters will be assessed at the start of each of the 3 experimental sessions. The participants will, then, vape sham-puffs (**cessation session**), nicotine free-puffs (**nicotine free session**) and

nicotine puffs (**regular consumption session**). During acute exposition, we will monitor at each puff any feelings of throat irritation, burn taste and Borg perception scale items (cough, chest tightness, breathlessness, secretions and wheezing). This acute exposition will be followed by clinical cardiorespiratory parameters assessment, lung function tests and maximal cycle ergometer test.

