3.3 Project plan and various step

The 5h-sessions will take place in the morning at the Hôpital Erasme. During each session, participants will be tested before and after acute exposure at the Cardiology Laboratory (ULB – Pr. [name]) for: 1) noninvasive continuous hemodynamic parameters (Electrocardiogram monitoring (AdInstrument[®]) and a beat-to-beat hemodynamic monitoring system¹⁷ Finapres Medical Systems[®]) 2) continuous respiratory rhythm, end-tidal carbon dioxide and blood oxygen saturation (Capnostream[®]);²⁸ 3) transcutaneous oxygen and carbon dioxide partial pressures (Perimed[®]);¹⁰ 4) skin microcirculatory blood flow by means of laser Doppler perfusion monitoring (continuous vascular conductance, heat test, acetylcholine and sodium nipride iontophoresis) (Perimed[®]);¹⁸ 5) Fractional exhaled carbon monoxide will be assessed at the start of each experimental session using a Smokerlyzer (SineFuma[®], Breda, Holland); 6) arterial stiffness indices (Sphygmocor[®]);²⁹ 7) exhaled breath condensate (Viasys Ecoscreen[®]);¹⁹ 8) Urine and 9) venous blood sample. Then, the participants will be directed to the Laboratory of Exercise Physiology, Faculty of Motor Sciences (ULB – Pr. [name]) to perform assessment of: 10) lung function tests plus capillary and membranous lung diffusing capacity as well as maximal ergometer cycle test²⁰ (details in appendix) (figure 2). After completion of clinical study in all participants, biological samples will undergo proteomics²¹ (ULB – Pr. [name]) and metabolomics²² (UMons – Pr. [name]) analysis (details in appendix).

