3.3.2 Continuous respiratory rhythm, end-tidal carbon dioxide and blood oxygen saturation

Continuous, non-invasive, real-time respiratory status monitoring of end-tidal CO₂ pressure, O₂ saturation in arterial blood, respiration rate, and pulse rate will be assessed with the Capnostream 35 monitor[©] (Oridion Medical Ltd, Jerusalem, Israël) throughout all the experimental sessions duration.

3.3.3 transcutaneous oxygen and carbon dioxide partial pressures

A PeriFlux system 5000 (Perimed[©], Järfälla, Sweden) will explore transcutaneous oxygen (O₂) and carbon dioxide (CO₂) partial pressures by means of a PF 5040 unit and a dual transcutaneous O₂ and CO₂ partial pressures E5280 electrode. After wiping the area with alcohol, a TC 550 fixation ring (Perimed[©], Järfälla, Sweden) will be applied to the skin in the medial side of the right arm (lower third and 5 cm distal to the antecubital fossa) at the level of the heart. Four drops of contact liquid (TC 560, Perimed[©], Järfälla, Sweden) will be instilled

inside the TC 550 fixation ring. Avoiding superficial vessels and body hair, the electrode will be placed at the same location for each of the two sessions on the basis of multiples pictures taken during the experimental session. Transcutaneous O₂ and CO₂ partial pressures values will be considered stable when variations did not exceed ± 2 mmHg within 1 min. Electrode remembranring will be done every two sessions.

3.3.4 skin microcirculatory blood flow by means of laser Doppler perfusion monitoring

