3.3.13 Sample size calculation

The primary objective of this study is to determine whether e-cigarette vaping cessation for five days increases transcutaneous oxygen partial pressure in regular users. Based on our previous researches, we assume that baseline mean transcutaneous oxygen partial pressure will be 80 mm Hg with a standard deviation of 7 mm Hg. To demonstrate that e-cigarette vaping cessation for five days significantly increases transcutaneous oxygen partial pressure, we assume a minimal rise in transcutaneous oxygen partial pressure of 10 mm Hg. We will need 16 patients, with 80% power to detect a group difference of 10 mm Hg in the change of transcutaneous oxygen partial pressure at a two-sided alpha-level of 0.05. We will enroll 21

participants in order to be sure to achieve a sufficient statistical power.

4. References

5. Etter JF. Throat hit in users of the electronic cigarette: An exploratory study. *Psychol Addict Behav*. 2016;30:93-100
7. Marseglia GL, Cirillo I, Vizzaccaro A, Klersy C, Tosca MA, La Rosa M, Marseglia A, Licari A, Leone M, Ciprandi G. Role of forced expiratory flow at 25-75% as an early

marker of small airways impairment in subjects with allergic rhinitis. *Allergy Asthma Proc.* 2007;28:74-8

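### No minimum period of usual vaping is stated before the regular-consumption session, so a residual cessation gain could bias the cessation-minus-regular contrast

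*Combined protocol and SAP*

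**What the plan says.** Section 3.1 describes a within-person comparison in which participants "will undergo three experimental periods in a random order". Cessation lasts five days, and the second condition is "nicotine free vaping for five days". The third is listed only as "regular e-cigarettes consumption", with no length. Measurements are taken before and after an acute exposure at each session. No visible section gives an interval between periods, a list of orders or a blocking scheme. Section 3.3 refers to material that is not shown ("details in appendix) (figure 2").

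Section 3.3.13 makes transcutaneous oxygen pressure the primary measure. It assumes a mean of 80 mm Hg, SD 7 and a 10 mm Hg rise, and powers on "a group difference of 10 mm Hg in the change of transcutaneous oxygen partial pressure". It arrives at 16 participants, with 21 to be enrolled.

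Section 3.2.1 asks for a negative urine cotinine dipstick and serum nicotine under 2 ng/ml at every session, without exempting the regular one. Section 3.2 removes a participant who violates the protocol, together with all of his data.

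**The concern.** Goal A in section 2 compares five days of cessation with continued vaping, so cessation minus regular is a core contrast. Regular consumption is the only condition with no defined run-in. A participant whose regular session comes soon after the cessation session could be measured as a regular user while part of the cessation gain remains. The regular level would then be too high and the estimated benefit of stopping too small.

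The nicotine-free contrast is less exposed, because five days of that condition precede its session. What is at stake is the size of the estimate, not a false positive. A missing run-in cannot be supplied once the data are collected.

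**Working it through.** **Inputs.** From 3.3.13: effect 10 mm Hg, SD 7, N 16 and 21. From 3.1: three conditions in random order. Assumed, because the documents give no value: the share λ of the gain still present at a regular session that follows cessation, and the within-person correlation (0 to 0.5).

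**1. The plan's own figure.** Two independent groups, normal approximation: n per group = 2 × (1.96 + 0.84)² × 7² / 10² ≈ 7.7, rounded up to 8, so 16 in total. The stated number reproduces, although the formula is for two groups and not for a crossover. The present point does not alter it.

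**2. How often regular follows cessation.** With C, N and R for cessation, nicotine-free and regular, the six orders are CNR, CRN, NCR, NRC, RCN and RNC. R comes directly after C in CRN and NCR. That is 2/6 of the orders, or 7 of 21 on average. Under simple randomisation the 5th to 95th percentiles of Binomial(21, 1/3) are 4 and 11.

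**3. Expected contrast in session level.** Contrast = 10 − 10 × λ × 1/3.

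| λ (assumed) | Contrast, mm Hg |
|---|---|
| 0.10 | 9.67 |
| 0.25 | 9.17 |
| 0.50 | 8.33 |
| −0.10 (rebound vaping) | 10.33 |
| −0.25 (rebound vaping) | 10.83 |

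**4. Effect on inference.** In simulated trials of 21, analysed with participant, period and condition, 95% intervals contain the true 10 mm Hg in about 95%, 92 to 93%, and 83 to 89% of trials at λ = 0.10, 0.25 and 0.50. Even at 8.33 mm Hg, a paired t-test with 21 participants has power 0.956 if the SD of the difference is 7 × √2 = 9.90 (correlation 0), and 0.999 if it is 7.0 (correlation 0.5).

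**5. What a five-day lead-in does.** Suppose 25% or 50% of the gain is left after one day of usual vaping and fades at a constant daily rate. After five days, 0.25⁵ = 0.001 or 0.5⁵ = 0.031 is left. The contrast is then 10 − 10 × 0.001/3 = 10.00 or 10 − 10 × 0.031/3 = 9.90.

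**6. What blocking does.** Three blocks of six orders put R directly after C in 3 × 2 = 6 participants. A further three-order Latin square adds 0 (CNR, NRC, RCN) or 2 (CRN, RNC, NCR). The total is 6 or 8 of 21, with a mean of 7, so the expected bias in step 3 is unchanged. Each condition does fall 7 times in each period, so condition is balanced against period.

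**7. If the endpoint is within-session change.** A residual shift s that moves both readings equally drops out: (post + s) − (baseline + s) = post − baseline. The wording in 3.3.13 leaves open whether the endpoint is this change or the session level.

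**8. The nicotine rule beside the lead-in.** Requiring usual nicotine vaping before the regular session, while 3.2.1 requires negative cotinine and low serum nicotine at every session, could make a compliant regular user a violator under 3.2. The purpose given in 3.2.1 is to confirm nicotine-free status, so the rule was probably meant for the cessation and nicotine-free sessions, but it does not say so.

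**The case against.** Participants have vaped exclusively for at least a year, and section 2 calls the comparator a pursuit of vaping. Habitual use is the default state, so it arguably needs no stated length, and someone just off five days of abstinence is not plainly in regular consumption. Order is also not time: the one third in step 2 counts adjacent sessions, not days between them, and a few ordinary days would shrink any residue. Figure 2 may set the timing. These arguments limit the size. They do not supply a minimum number of days, and the serum checks in 3.2 and 3.2.2 do not establish that usual vaping had resumed.

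A reader might infer more than the documents support:

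- **That carryover is shown.** It is not. Section 1.2 reports that acute vaping "induced a sustained transcutaneous hypoxia", which makes high persistence after resumed vaping less likely, and rebound vaping would push the contrast the other way.
- **That the trial loses power.** The two-group formula with 16 participants gives 66% at 8.33 mm Hg, but every participant has all three conditions, and paired power is 96% or more with 21 (step 4).
- **That unblocked random order biases the contrast.** It does not. With simple randomisation and an assumed 2 mm Hg shift in session two, an ordinary paired interval covered the truth in 94.9% of simulated trials.
- **That electrode maintenance creates a session effect.** Section 3.3.3 says "Electrode remembranring will be done every two sessions", which can equally be a laboratory count across participants. No shift is documented, so the argument is not relied on here.
- **That the plan lacks a valid analysis.** No crossover model is visible, but that is missing detail and not a demonstrated error.

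**Conclusion.** The point holds as a gap in the visible design. Nothing in it prevents a regular session soon after cessation, and any residual gain would probably bias the level contrast toward zero. At assumed persistence of 10% to 25% the bias is 0.3 to 0.8 mm Hg out of 10. It reaches 1.7 mm Hg only if half the gain remained at the regular session of every participant in the exposed orders. These figures rest on equally likely orders, on sessions close in time and on an endpoint defined as session level. Confidence is medium, because the persistence values are assumptions and the schedule may be in material not shown. The change is still worth making before recruitment.

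**What to change.** 1. State in 3.1 that the regular session follows at least five days of usual vaping. This is the change that reduces carryover. In 3.2.1, limit the cotinine and serum nicotine rule to the cessation and nicotine-free sessions, so that compliant regular users are not removed under 3.2.
2. For precision only, allocate the six orders in permuted blocks, with three blocks of six plus one three-order Latin square for the 21 participants ("We will enroll 21" in 3.3.13). Include period with condition and participant in the analysis.

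The cost is a few sentences, a randomisation list and slightly more calendar time, with no extra participants. If figure 2 or the appendix already sets a lead-in, only the nicotine rule and the blocking remain to be changed.

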3.2. Measures to ensure strict compliance of the study protocol

All the participants will sign a declaration on honor that they will respect the study protocol. Twelve hours fasting blood samples will be drawn during each experimental session at baseline and 1 hour after acute exposition. All blood samples will undergo serum nicotine, PG and GLY concentration analysis to confirm compliance of the study protocol.²³⁻²⁶ In case of a protocol violation, the participant will not be allowed to continue the study, and his full dataset will be discarded from the study.

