3.2.1 Serum nicotine concentration

At each experimental session, participants will be negative for urine cotinine (urine dipstick – detection threshold of 50 ng/ml – NarcoCheck[©])²³ and concentration of serum nicotine should be below 2 ng/ml, a value confirming the status of nicotine free vaping and the lack of significant nicotine exposure.^{24,27} Serum nicotine will be measured by means of a mass spectrometer with a jet stream electrospray ion source.

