3.2.2 Serum propylene glycol and glycerol

Since serum PG and GLY normal values in regular vapers are unknown, we will take means of PG and GLY serum concentration measured during the **regular consumption session**

and nicotine free session for further comparison to the value obtained during the **cessation session**, in order to confirm the compliance to the study protocol. Serum values of PG and GLY will be assessed using gas chromatography with a flame ionization detector.²⁵

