3.3.4.3 Heat test

“Using another laser probe (PF 457, Perimed) at the level of right distal arm (anterior side) that will be positioned at the beginning of the recordings. Maximal skin microvascular vasodilatation will be measured after vaping or sham vaping using prolonged (20 minutes) local heating of the laser probe to 44°C. The use of the area under the blood flow/time curve (AUC) for assessing skin microvascular reactivity using Laser Doppler Perfusion Monitoring is well validated because it represents the global flow response to different physiological and pharmacological stimuli.”³³⁻³⁵ (CLINICS 2011;66(4):599-605)

3.3.5 fractional exhaled carbon dioxide

Fractional exhaled carbon monoxide will be assessed at the start of each experimental session using a Smokerlyzer (SineFuma©, Breda, Holland). Fractional exhaled carbon monoxide should be less than 5 ppm.³⁶

3.3.6 arterial stiffness indices

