3.3.12 Serum, urine and breath exhaled condensate metabolomics analysis

In order to better understand effects of regular e-cigarettes consumption on human metabolome and to confirm vaping cessation, serum, urine and breath exhaled condensate of our participants will undergo metabolomics analysis. This will be done using nuclear magnetic resonance spectrometry at the Department of Human Biology & Toxicology (University of Mons - Faculty of Medicine – Pr. [name]) as previously described.²²

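### Serum nicotine, PG and GLY are Goal A outcomes and also the compliance assays; violators' data are discarded, no all-randomised analysis is described, and the nicotine limit as written covers the regular session

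*Combined protocol and SAP*

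**What the plan says.** The document is a combined protocol and SAP. Its only statistical text is the sample size paragraph (Section 3.3.13), which names no analysis population.

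- **Outcome.** Section 2, first Goal A, compares five days of cessation with continued vaping and expects that cessation "Decreases serum PG/GLY and nicotine concentrations".
- **Compliance.** Section 3.2: "All blood samples will undergo serum nicotine, PG and GLY concentration analysis to confirm compliance of the study protocol".
- **Consequence.** Section 3.2: "In case of a protocol violation, the participant will not be allowed to continue the study, and his full dataset will be discarded".
- **Nicotine limit.** Section 3.2.1 says that the "concentration of serum nicotine should be below 2 ng/ml, a value confirming the status of nicotine free vaping". The same sentence opens with its scope: "At each experimental session, participants will be negative for urine cotinine".
- **PG/GLY.** Section 3.2.2 says normal values in vapers are unknown, so "we will take means of PG and GLY serum concentration measured during the" regular consumption and nicotine free sessions, and compares the cessation value with them to confirm compliance. It gives no cut-off and does not say whether the comparison is made per person or per group.
- **Sessions.** In Section 3.1 every participant goes through cessation, nicotine free and regular consumption periods in random order, with nicotine puffs in the last of these.

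**The concern.** When a measurement decides who stays in the dataset, testing that measurement among those who stay is partly circular. A participant whose cessation sample is high is the one most likely to be removed, so the remaining values are low partly because of the removal. Real abstinence may also lower them, but the filtered data cannot separate the two. Because the whole dataset goes, the primary oxygen comparison is also restricted to compliers, and without the excluded data nobody can check what the exclusion did.

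A second defect is purely textual. The cotinine and nicotine limits are written for every session, while one session consists of vaping nicotine. Combined with the discard rule, that would remove participants for following the protocol.

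**Working it through.** **1. The plan's own sample size.** Section 3.3.13 gives a difference of 10 mm Hg, SD 7, two-sided alpha 0.05 and 80% power. The two-group normal formula gives 2 x (1.96 + 0.84)^2 x 7^2 / 10^2 = 7.7, so 8 per group and 16 in total, which matches the stated 16. Enrolment is 21, leaving room for 5 discards.

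**2. Nicotine.** Suppose the limit applies to the cessation session and a breach is a violation. Every kept cessation value is then below 2 ng/ml, whatever cessation did. As an illustration, assume a regular-session median of 5 ng/ml, compliers' cessation median 0.5, log-SD 0.6, and violators unchanged from their regular level. Mean fall in ng/ml:

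| Violators | All randomised | Kept only | Ratio |
|---|---|---|---|
| 10% | 4.85 | 5.41 | 1.12 |
| 20% | 4.31 | 5.39 | 1.25 |
| 30% | 3.77 | 5.37 | 1.42 |

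If the limit also binds the regular session, both sides of the contrast lie below 2 ng/ml and the rule works against a fall.

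**3. PG/GLY.** A group-level check removes nobody and causes no bias. For an individual check the cut-off must be assumed. Hypothetical inputs: lognormal values, CV 0.6, n = 21, within-person correlation 0 to 0.6, no true fall. The test compares log cessation with the mean of the two log vaping values, two-sided 0.05, counting decreases.

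| Participant kept if cessation value is | Mean kept of 21 | Significant decrease |
|---|---|---|
| anything (no filter) | 21 | 2-3% |
| at or below vaping mean + 2 SD | 19.9 | 4-5% |
| at or below vaping mean + 1 SD | 18.0 | 8-14% |
| below the group vaping mean | 12.7 | 22-58% |
| below the person's own vaping mean | 11.1-11.4 | 97-98% |

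A t-test on unlogged values gives higher rates: 3-4%, 6-8%, 13-24%, 31-77% and 97-99%. With a true 50% fall, at least 98% of unfiltered trials are already significant, so the filter adds little.

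**4. Primary outcome.** Oxygen shifts only if its change is related to PG/GLY change. With SD of change assumed 9.9 mm Hg (7 x sqrt 2) and correlations of -0.2 to -0.4 with log PG/GLY change, the shift across the four unlogged-scale cut-offs is 0.0-0.8 mm Hg with a 50% fall, 0.0-1.6 with a 30% fall and 0.2-2.9 with no fall, against a target of 10.

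**5. Numbers kept.** With violation probability p in each of the two restricted sessions (cessation and nicotine free), the mean kept is 21(1 - p)^2: 19.0, 17.0 and 15.2 at p = 5%, 10% and 15%. It equals 16 at p = 1 - sqrt(16/21) = 12.7%. A paired test with 15 kept still has power 0.95 at SD of change 9.9.

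**6. Leaving the study.** Suppose a violation is detected at the session concerned and later sessions are lost. With six equally likely orders, the cessation and regular sessions are both observed in 3 of 6 orders if the violation is in the cessation session, and in 2 of 6 if it is in the nicotine free session. Keeping data already collected therefore does not fully restore an all-randomised comparison.

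**The case against.** **The PG/GLY check may exclude nobody.** Where the plan wants an individual limit it states one: 2 ng/ml for nicotine, a dipstick threshold for cotinine, and "Fractional exhaled carbon monoxide should be less than 5 ppm" (Section 3.3.5). Section 3.2.2 states none, so a group-level check is a natural reading. This stands. A reader might infer from the 97-98% row that the plan guarantees a spurious PG/GLY fall. The documents do not support that: all four cut-offs are assumptions, the own-mean rule discards nearly half the participants when there is no effect, and a complete absence of effect after five days without vaping is an unlikely setting. What remains is that Section 3.2 sets its consequence per participant and Section 3.2.2 does not say which reading applies.

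**The nicotine limit may not create a fall.** This is also partly right. A reader might conclude that the kept cessation-to-regular ratio cannot exceed 2/10 = 0.20 if the regular mean were 10 ng/ml. That needs an assumed mean and a limit that spares the regular session, which is not what Section 3.2.1 literally says.

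**A complier analysis suits a physiological question.** It does, and it may be the main analysis. Discarding may also mean only exclusion from analysis, not destruction. Neither point answers the lack of any described analysis including violators.

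**Section 3.2.1 is a drafting slip.** Probably so, since its own clause refers to nicotine free vaping. The text still needs correcting because a discard rule hangs on it.

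**Conclusion.** The point holds in a limited form. The structural fault is plain in the text: three assays serve as both outcome and filter, violators' full datasets are dropped, and no all-randomised analysis is described. For nicotine the built-in element follows from the rule if the limit applies to the cessation session and a breach is a violation. For PG/GLY it ranges from nil to dominant depending on an unstated rule, and its size cannot be derived from the documents, which give no violation rate and no serum distributions.

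A reader might go further and conclude that the primary oxygen result is invalid or the trial underpowered. The working does not support that. The oxygen shift is conditional and probably small against 10 mm Hg; the largest figure, 2.9, needs no PG/GLY fall at all. The average number kept drops below 16 only above about 12.7% violations in each restricted session, and paired power remains high there.

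The firmest defect is the conflict between Section 3.2.1 and Section 3.1, which needs no assumption beyond reading the sentence literally together with the discard rule. Overall this should be corrected before samples are assayed; it does not threaten the primary objective.

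**What to change.** 1. **Section 3.2.** Replace the discard clause with: *All collected data are kept. The primary outcome is analysed in all randomised participants with data, each session as assigned, and also in compliant participants; which is the main analysis is fixed before any sample is assayed. The number, session and reason for each exclusion are reported.* Reconcile the rule that violators may not continue with this analysis, since later sessions would otherwise be missing selectively.
2. **Serum PG, GLY and nicotine.** Report them unfiltered in everyone, as a manipulation check.
3. **Section 3.2.2.** Before assay, state that the PG/GLY check is group-level or, if individual, give its cut-off. Use pre-puff samples only and apply the check blind to the oxygen results.
4. **Section 3.2.1.** Reconcile with Sections 2 and 3.1 on which sessions the cotinine and nicotine limits cover.

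The cost is wording, one rule fixed in advance and one extra analysis of data already collected. The downside is that non-compliers may dilute the all-randomised estimate, by an amount the documents do not allow to be estimated; the complier analysis is still reported.
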